3.2.3 Exploratory efficacy variables

Other efficacy variables are:

- Time from randomisation to first occurrence of any event from the composite of all-cause death, MI or stroke
- Time from randomisation to first occurrence of stroke
- Time from randomisation to first occurrence of any event from the composite of all-cause mortality, MI, stroke, intracranial haemorrhage and fatal bleeding (irreversible harm events)
- Time from randomisation to the first occurrence of any event from the composite of arterial and venous thrombotic events that fulfils any SAE criteria
- Time from randomisation to first occurrence of coronary arterial revascularisation
- Time from randomisation to first occurrence of any event from the composite of ALI and major amputation of vascular aetiology
- Time from randomisation to first occurrence of any event from the composite of urgent peripheral arterial revascularisation, venous thrombotic event, ALI and major amputation of vascular aetiology

- Time from randomisation to first occurrence of any event from the composite of all-cause mortality, MI, stroke, ALI and major amputation of vascular aetiology
- Time from randomisation to first occurrence of any event from the composite of CV death, MI, stroke, ALI, major amputation of vascular aetiology and venous thrombotic event
- Time from randomisation to first occurrence of any event from the composite of CV death, MI, stroke, ALI, major amputation of vascular aetiology and urgent peripheral arterial revascularisation
- Time from randomisation to first occurrence of any event from the composite of all-cause mortality, MI, stroke, ALI, major amputation of vascular aetiology, venous thrombotic event, urgent peripheral arterial revascularisation and coronary revascularisation
- Health care resource utilisation and utilities assessed by EQ-5D questionnaire to support health technology assessment and health economic modelling.

3.3 Safety variables

3.3.1 Adverse events

AEs of interest (i.e., dyspnoea, renal impairment, bradyarrhythmia, gout, and pneumonia) and DAEs (Discontinuations of Study Medication due to Adverse Event) will be collected from randomisation throughout the study until and including the Study Closure Visit (SCV).

All SAEs will be recorded from the time of informed consent throughout the study until and including the SCV. Events adjudicated to the endpoint events non-fatal MI, primary ischaemic stroke or CV death, although qualifying as SAEs, will only be reported as primary endpoint events in the Clinical Study Report.

Section 6.4 in the Clinical Study Protocol (CSP) gives more detailed information on adverse event data collection.

3.3.2 Bleeding events

Bleeding events that are self-limited, and do not prompt medical evaluation or intervention, need not to be reported. For all bleeding events that are unexpected or of unanticipated quantity, the investigator will complete information on the eCRF specific to that bleeding event. In addition, for all reported bleeding events relevant information will be compiled and sent to the CEC for central adjudication according to the following bleeding definitions: TIMI, PLATO and BARC. Additional details can be found in the CEC Charter.

Additionally, all bleeding events (including haemorrhagic stroke) fulfilling the SAE criteria will be reported as SAEs by the sponsor to the health authorities. If the adjudication of a stroke event unveils a haemorrhagic stroke not yet reported as SAE, it will be reported as SAE to the health authorities. Further details can be found in Section 6.4.5 in the CSP.

Specific focus will be on the following bleeding variables, from time of randomisation:

- Time to first TIMI Major bleeding event (primary safety objective)
- Time to first TIMI Major or Minor bleeding event
- Time to first PLATO Major bleeding event
- Time to permanent discontinuation of study medication due to any bleeding event.

3.4 Treatment compliance

Patients will be asked to return all unused study medication and empty packages to the clinic at each visit. The number of dispensed and returned pills (determined by pill count) will be recorded in the eCRF. Based on the pill counts, the percentage treatment compliance will be calculated as the number of pills taken (dispensed minus returned) relative to the expected number of taken pills. The expected number of pills taken will be calculated as:

$$(\text{number of pills to be taken daily}) \times (\text{number of days between visits} - \text{number of days of planned interruption})$$

The number of pills to be taken daily is 2, initially either 2 ticagrelor 90 mg or 2 ticagrelor 90 mg placebo, while after Clinical Study Protocol Amendment No 1, either 2 ticagrelor 60 mg or 2 ticagrelor 60 mg placebo.

4. ANALYSIS METHODS

4.1 General principles

Clinical events reported after database lock will not be included in the primary efficacy and safety analysis.

For time to event variables, treatments will be compared using a Cox proportional hazards model with a factor for treatment group, using the Efron method for ties. Censoring principles are described in Section 4.1.1. The p-values (calculated using the Wald test), HR and 95% confidence intervals for the HR will be reported. Summary tables of these analyses will also include the number of patients with an event and Kaplan-Meier estimates of the event rates per treatment group estimated at a time point determined on the basis of the available follow-up. Kaplan-Meier estimates of the cumulative proportion of patients with events will be estimated and plotted, with the number of patients at risk indicated below the plot at specific time points. If the total number of events in an endpoint or subgroup category is <15, only percentage of patients with events will be presented, but no Kaplan-Meier estimates, HRs, confidence intervals or p-values.

The primary and secondary efficacy variables will be included in a confirmatory testing procedure described in Section 4.2.3. No further multiplicity adjustment will be made to

confidence intervals or p-values. Analyses of efficacy or safety variables that are not part of the confirmatory analyses are considered exploratory and any p-value and confidence interval will be used as a measure of precision only.

In addition to specific analyses and presentations that are detailed in the following sections, results will be summarised using descriptive statistics, including the number of patients, mean, standard deviation, median and range as appropriate. For categorical variables counts and percentage per treatment group will be presented. Summaries of continuous variables will be based on non-missing observations. Percentage for categorical variables will be calculated based the total number of patients in the treatment group, i.e. the denominator includes the number of patients with missing values for the variable.

Demographic characteristics, qualifying risk factors and other specific medical and surgical history will be summarised for the FAS using descriptive statistics.

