5.10 Study committees

5.10.1 Executive Committee (EC)

The EC will be responsible for the overall design, including the development of the protocol and any protocol amendments, supervision, interpretation and reporting (presentations at international congresses and publications in peer reviewed journals) of the study. The EC will make recommendations to AstraZeneca with regard to early stopping or modifications of the study based on the information received from the DMC. The EC will be comprised of designated international academic leaders and non-voting members of the Sponsor, and will operate under a separate charter.

To achieve an appropriate subgroup final distribution ratio, the Executive Committee will monitor particular subgroups and primary event rates and may cap enrolment to a particular subgroup based on the overall distribution and event rates. In particular, the enrolment of patients without ASA background treatment will be capped if it is considered inappropriately high or more than 5%.

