1.1.4 Safety objectives

The overall safety objective of this study is to assess the safety and tolerability of long-term therapy with ticagrelor compared to placebo in patients with T2DM at high risk of CV events, with or without background low-dose aspirin therapy. Bleeding events will be analysed using the Thrombolysis in Myocardial Infarction Study Group (TIMI), PLATO (PLATElet inhibition and patient Outcomes) and the Bleeding Academic Research Consortium (BARC) definitions. Specific focus will be on:

- Time to first TIMI Major bleeding event (primary safety objective)
- Time to first TIMI Major or Minor bleeding event
- Time to first PLATO Major bleeding event
- Time to permanent discontinuation of study medication due to any bleeding event.

Non-serious AEs of interest (i.e. dyspnoea, renal impairment, bradyarrhythmia, gout, and pneumonia), adverse events that leads to permanent discontinuation of study medication (DAEs) and all serious adverse events (SAEs) will be reviewed within the context of the earlier safety experience with the drug.

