4.2.1.2 Exploratory analyses and subgroup analyses of the primary efficacy variable

Subgroup analyses on the primary efficacy variable, and its components, will be performed to evaluate variation of treatment effect. The subgroups in [Table 1](#) will be examined in Cox regression models with a factor for treatment. Kaplan-Meier estimates, hazard ratios and 95% confidence intervals will be reported for each subgroup category if at least 15 events have occurred within the subgroup category. A test of interaction between treatment and each subgroup will be performed in a Cox proportional hazards model with factors for treatment,

subgroup and the interaction between treatment and subgroup for each subgroup where at least 15 events have occurred in each category.

Table 1 **Characteristics and categories for subgroup analysis of the primary composite endpoint**

Characteristic	Categories
Age (years)	< 65, 65-75, >75
Sex	Male, Female
Race	White, Black or African American, Asian, Other
BMI (kg/m ²)	≤ 30, >30
Geographic region	Asia and Australia, Europe and South Africa, North America, Central and South America
ASA use at randomisation	Yes, No
ASA dose at baseline (mg)	≤81, >81
HbA1c at baseline (%)	≤ 7, > 7
eGFR (MDRD) at baseline (mL/min/1.73 m ²)	≤ 60, > 60
Insulin use at baseline	Yes, No
History of Angina	Yes, No
Multivessel Coronary Artery Disease (>1 vessel)	Yes, No
History of PCI	Yes, No
Type of stent	PCI and any DES (including patients with both DES and BMS), PCI and BMS, PCI without stent implantation
History of CABG	Yes, No
History of Coronary Arterial Revascularisation	Yes, No
Statin use at baseline	Yes, No
PPI use at baseline	Yes, No
Current smoker	Yes, No
Duration of diabetes (years)	≤10, >10
History of any diabetes complications at baseline	Yes, No
Number of prior diabetes complications	0, 1, 2, 3-4
History of Peripheral Arterial Occlusive disease	Yes, No
History of Poly-vascular disease	Yes, No
Number of prior vascular beds	1, 2, 3
Time since most recent PCI (years)	<1, 1-3, >3

Characteristic	Categories
Time since most recent CABG (years)	≤ 5 , > 5

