4.2.6.2 Time to event analysis of bleedings

Time to bleeding event variables will be analysed using the same methodology as for the efficacy variables as described in Section 4.1.

Explorative analysis of time to bleeding for selected subgroups will be performed for the main bleeding categorisations (TIMI major, TIMI major or minor, and PLATO major). Subgroups will be the groups defined for the efficacy analysis in Section 4.2.1.2.

Sensitivity analysis of TIMI major bleeding to address the consistency of the overall effect of ticagrelor on bleeding compared to the 60 mg dose will be performed with a Cox proportional hazards model with time dependent covariates, as described in Section 4.2.1.1 for the primary variable.

Furthermore, a sensitivity analysis of TIMI major bleeding on-treatment in patients randomised to ticagrelor 60 mg or ticagrelor 60 mg placebo and in patients randomised to ticagrelor 90 mg or ticagrelor 90 mg placebo will be performed. These analyses include events that occur up to and including 7 days after last randomised dose of study drug, and event free patients will be censored at the earlier of 7 days after last randomised dose of study drug, last contact, death, SCV or withdrawal of consent.

A landmark analysis of TIMI major bleeding to explore the consistency of treatment effect over treatment dose will be performed. In the analysis, the incidence of TIMI major bleedings

when the patients are treated with ticagrelor 90 mg or ticagrelor 90 mg placebo, and when patients are treated with ticagrelor 60 mg or ticagrelor 60 mg placebo for patients who were event free up to the day of the first 60 mg dose are examined.

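### Bleeding categories with fewer than 15 events, realistically including TIMI major bleeding in patients without ASA, get crude percentages only, with no comparative estimate or interval

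*SAP*

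**What the plan says.** SAP 4.1 sets a minimum count for time-to-event results: "If the total number of events in an endpoint or subgroup category is <15, only percentage of patients with events will be presented". The hazard ratio, its interval, the p-value and the Kaplan-Meier estimate are all left out in that case. The count is a total, so the two arms are added together.

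SAP 4.2.6.2 brings bleeding under this rule: "Time to bleeding event variables will be analysed using the same methodology as for the efficacy variables as described in Section 4.1". It also plans exploratory subgroup analyses of TIMI major, TIMI major or minor, and PLATO major bleeding: "Subgroups will be the groups defined for the efficacy analysis in Section 4.2.1.2". Table 1 of that section includes ASA use at randomisation, yes or no. SAP 4.2.1.2 runs the interaction test only "for each subgroup where at least 15 events have occurred in each category".

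The SAP gives no exemption for safety and no substitute method for small counts. Below the threshold the percentages remain, and SAP 4.2.6.1 separately summarises bleeding events by arm and gives total event numbers.

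The safety objective in SAP 1.1.4 covers patients "with or without background low-dose aspirin therapy". Protocol 5.10.1 limits the size of the second group: "the enrolment of patients without ASA background treatment will be capped if it is considered inappropriately high or more than 5" per cent.

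Protocol 12.2.1 and 12.2.2.1 plan a hazard ratio, interval and p-value for the bleeding endpoints, and time-to-event analysis of further bleeding categories, with no minimum count. SAP section 6 does not list the minimum as a change from the protocol.

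**The concern.** A floor on the event count is a sensible guard against unstable Wald hazard ratios. The weakness is in what replaces them. A crude percentage per arm carries no measure of precision, although SAP 4.1 gives precision as the purpose of intervals outside the confirmatory tests. It also ignores time at risk. SAP 4.1.1 ends bleeding follow-up 7 days after the last dose, and stopping study drug because of bleeding is itself a safety variable (SAP 3.3.2), so on-treatment time may differ between arms. Two percentages cannot reflect that; an incidence per patient-year can.

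The place where this matters most is the no-ASA group. It is part of the safety population, it is deliberately kept small, and TIMI major bleeding is the primary safety objective. If that cell falls below 15 events, the report shows two percentages and no ASA-use interaction test.

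**Working it through.** **Inputs from the documents.** 19000 patients, 1:1 allocation, average follow-up 40 months (SAP 1.3); no-ASA cap near 5% (Protocol 5.10.1); threshold of 15 events, arms combined (SAP 4.1); fatal bleeding of 0.1% to 0.3% per arm in the two earlier ticagrelor trials described in Protocol 1.4.

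**Not in the documents.** There is no expected bleeding count, TIMI major rate or intracranial haemorrhage rate, and no reason given for choosing 15. So there is no bleeding figure of the plan's own to reproduce. The 1385 primary events do reproduce (Schoenfeld: 1386 for HR 0.84, two-sided 4.96%, 90% power) but do not bear on this point.

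**Step 1: break-even in the no-ASA group.** 0.05 × 19000 = 950 patients. Risk needed for 15 events: 15/950 = 1.58%, or 15/(950 × 40/12) = 0.47 per 100 patient-years over full follow-up.

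**Step 2: chance of falling below 15.** Expected events = n × pooled cumulative on-treatment risk; the chance is Poisson P(X ≤ 14). The risks, and the shares below 5%, are assumptions.

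| No-ASA share (n) | Break-even risk | Risk 1.0% | Risk 1.5% | Risk 2.0% | Risk 3.0% |
|---|---|---|---|---|---|
| 5% (950) | 1.6% | 9.5 events, 94% | 14.3, 54% | 19, 15% | 28.5, 0.2% |
| 3% (570) | 2.6% | 5.7, >99% | 8.6, 97% | 11.4, 82% | 17.1, 27% |
| 2% (380) | 3.9% | 3.8, >99% | 5.7, >99% | 7.6, 99% | 11.4, 82% |

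A second route, also on assumed inputs (HR 2, 2.7 on-drug years, placebo rate 0.3 to 0.5 per 100 patient-years), gives 475 × 2.7 × 0.003 × 3 = 11.5 to 475 × 2.7 × 0.005 × 3 = 19.2 events at the 5% share. The chance of fewer than 15 is then 81% to 14%, consistent with the first row.

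**Step 3: fatal bleeding, whole trial.** Threshold risk: 15/19000 = 0.079%. At 0.1%, 0.2% and 0.3%, 19, 38 and 57 events are expected; P(<15) is 15%, below 0.001% and essentially 0. If on-treatment censoring kept only 60% of events (an assumption), 11.4, 22.8 and 34.2 would be expected; P(<15) is 82%, 3% and about 0.

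**Step 4: what an exact interval would show.** Given total d = a + b, the ticagrelor count a is binomial with probability π. Clopper-Pearson limits for π convert to the rate ratio as π/(1 − π) × (placebo patient-years / ticagrelor patient-years). With equal patient-years:

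| Ticagrelor : placebo | Rate ratio | Exact 95% CI | p |
|---|---|---|---|
| 7 : 7 | 1.0 | 0.30 to 3.34 | 1.0 |
| 11 : 3 | 3.7 | 0.97 to 20.5 | 0.057 |
| 12 : 2 | 6.0 | 1.34 to 55.2 | 0.013 |
| 13 : 1 | 13 | 1.95 to 552 | 0.0018 |

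Some splits below the threshold thus have an interval that excludes 1. Nor does precision change sharply at 15: at an even split the Wald factor exp(1.96 × √(4/d)) is 2.85 with 14 events and 2.75 with 15.

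**Step 5: efficacy for comparison.** Over 40 months at 2.5% and 2.1% (0.84 × 2.5%) a year, 9500 per arm gives about 1402 primary events, so 950 × 1402/19000 = 70 in the no-ASA group. The rule does not affect the primary endpoint there.

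**The case against.** The case for leaving the rule alone has substance.

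- **Data are not lost.** A reader might infer that sparse bleeds would be left with no estimate at all, or that imbalances would be hidden. The documents do not support that. Percentages by arm, bleeding summaries and total events are all presented, and a 12 : 2 split would be plain to see in arms of near-equal size.
- **Fatal bleeding mostly escapes.** A reader might infer from the 6, 11 and 12 fatal bleeds per arm in the earlier placebo-controlled trial (Protocol 1.4) that fatal bleeding would be suppressed here. The rule adds the arms, so those comparisons total 6 + 12 = 18 and 11 + 12 = 23, both above 15. Fatal bleeding also sits inside the irreversible-harm composite, which is planned for Cox analysis.
- **There is no separate no-ASA objective.** The wording about ASA describes who is in the safety population. ASA use is one of many exploratory subgroups, and fatal bleeding by ASA use is not planned.
- **Lopsided splits are not the expected ones.** If the true ratio were 2, 14 events would split 12 : 2 or more extremely toward ticagrelor about 10.5% of the time (binomial, probability 2/3).
- **A sparse interaction test says little.** With 14 events in one category the standard error of the log hazard ratio is at least √(4/14) = 0.53, so 80% power needs a ratio of hazard ratios near exp(2.8 × 0.53), about 4.5, even ignoring error in the other category.

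All five stand, and they limit the point. They do not answer what remains: percentages ignore unequal on-treatment time and carry no interval, while an exact method is valid at any count.

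**Conclusion.** The point holds as a modest reporting gap. The rule covers bleeding endpoints and the ASA-use subgroup, and below 15 events it removes every comparative estimate and interval without a substitute that accounts for time on treatment.

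For TIMI major bleeding in the no-ASA group this is a realistic outcome: 94% to 15% likely at assumed cumulative risks of 1.0% to 2.0% with 950 patients, and more likely if the group is smaller. At 3.0% and the full 5% share it would almost never happen. The range is wide because the documents give no TIMI major rate.

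For fatal bleeding across the trial it is unlikely, unless the risk is near 0.1% and on-treatment censoring removes many events. Nothing can be said about intracranial haemorrhage, for which no rate is given. The primary and secondary confirmatory tests are unaffected.

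**What to change.** Add to SAP 4.1, in substance: *for adjudicated bleeding endpoints, and for TIMI major bleeding by ASA use at randomisation, when a category has fewer than 15 events, present descriptively the number of events, on-treatment patient-years, incidence per 100 patient-years by arm, and an exact conditional 95% confidence interval for the rate ratio.*

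Keep the 15-event rule as it is for all other subgroups. Leave the condition on the interaction test in place as well: a test run at any count would have almost no power here and could be misread as evidence of no interaction.

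The cost is a sentence in the SAP, minor programming, and some wide intervals in the report.

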4.1.1 Censoring

The executive committee will monitor the accrual of the number of primary events and when appropriate predict and define a primary analysis censoring date (PACD) at which time the pre-defined target number of events for the primary composite endpoint are expected to have occurred.

The PACD will be the common date at which all patients who are event free for the given endpoint and have not withdrawn consent for participating in the study will be censored in efficacy time-to-event analyses. Events that occur after the PACD but before the SCV will also be collected and adjudicated. These events will be included in sensitivity analyses but not in the primary analysis. Events that occur after SCV will be described in text or tabulated descriptively.

Patients who have not had the event(s) in question will be censored at the earlier of (1) the PACD and (2) the last study contact when all components of the endpoint in question were assessed. In the analysis of CV death and composites including CV death censoring will occur at the earlier of (1), (2) and (3) the date of death from non-cardiovascular causes. For endpoints not including death, all deaths are censoring events.

Complete endpoint information will be pursued with every effort for all patients regardless of their study medication status, unless they exercise their right to withdraw consent. Patients who have a non-fatal event will continue study follow-up. For patients who withdraw consent and for whom only vital status (known to be alive at study closure, or date of death) may be obtained from public records, the occurrence of all components of the primary endpoint cannot be assessed. Thus, in the main analyses patients will be censored at the time when all elements of the endpoint were assessed for those patients who withdraw consent and for whom only vital status is known from public records. However, the determination of all-cause death will utilise all publicly known mortality data, even that extending beyond date of consent withdrawal. The vital status information will be included in the analysis of all-cause death as a single endpoint, and in sensitivity analysis and tabulations.

Similarly, complete information on the primary endpoint may not be obtained for patients who are lost to follow-up (LTFU). Any such patient will be censored in the analysis of the primary composite endpoint at the last contact where all elements of the endpoint were assessed. A patient will not be recorded as LTFU until the end of the study, after every allowable effort to get in contact has been made. Hence, it is anticipated that the number of patients LTFU will be limited.

In safety time-to-event analysis of bleeding and discontinuation of study drug due to bleeding, patients not having suffered any bleeding event in the given category will be censored at the earlier of SCV, 7 days after last dose of study drug, death, last contact or withdrawal of consent.

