12.2.1 Efficacy analysis

All efficacy analyses will be based on the ITT principle using the FAS, including only adjudicated endpoint events. Investigators are instructed to report all potential endpoint events in the eCRF, even those that may not meet strict endpoint definitions, to ensure all potential events are reviewed and adjudicated by the CEC.

For time to event variables, treatments will be compared using a Cox proportional hazards model with a factor for treatment group, using the Efron method for ties. Censoring principles are described in Section 12.2.4. The p-value (calculated using the Wald test), hazard ratio (HR) and 95% confidence interval will be reported. Kaplan-Meier estimates of the cumulative risk will also be presented.

The family wise error rate will be controlled for the primary and secondary efficacy analyses by applying a hierarchical test sequence as described in Section 12.2.1.2. No other adjustments for multiple comparisons will be made.

As supportive analyses, data from patients with diabetes in PEGASUS (patients with MI within 1-3 years) and EUCLID (PAD patients) will be pooled and analyzed with and without

data from this study. These analyses will be described in a separate SAP and reported separately.

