12.2.4 Censoring

The EC will monitor the accrual of the number of primary events and when appropriate predict and define a PACD at which time the pre-defined target number of events for the primary composite endpoint are expected to have occurred.

The PACD will be the common date at which all patients who are event free for the given endpoint and have not withdrawn consent for participating in the study will be censored in efficacy time-to-event analyses. Events that occur after the PACD but before the SCV will also be collected and adjudicated. These events will be included in sensitivity analyses but not in the primary analysis.

Patients who have not had the event(s) in question will be censored at the earlier of (1) the PACD and (2) the last study contact when all components of the endpoint in question were assessed. In the analysis of CV death and composites including CV death censoring will occur at the earliest of (1), (2) and (3) the date of death from non-cardiovascular causes. For endpoints not including death, all deaths are censoring events. In safety time-to-event analysis of bleeding, patients not having suffered any bleeding event in the given category will be censored at the earlier of SCV, 7 days after last dose of study drug, death, last contact or withdrawal of consent.

Complete endpoint information will be pursued with every effort for all patients regardless of their study medication status, unless they exercise their right to withdraw consent. Patients

who have a non-fatal event will continue study follow-up. For patients who withdraw consent and for whom only vital status (known to be alive at study closure, or date of death) may be obtained from public records, the occurrence of all components of the primary endpoint cannot be assessed. Thus, in the main analyses patients will be censored at the time of consent withdrawal. However, the determination of all-cause death will utilise all publicly known mortality data, even that extending beyond date of consent withdrawal. The vital status information will be included in the analysis of all cause death as a single endpoint, in sensitivity analysis and tabulations.

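### Time to stopping study drug for bleeding is shown as 1 minus Kaplan-Meier with other final stops and deaths censored, so the displayed proportion overstates how many patients stop for bleeding

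*SAP*

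**What the plan says.** SAP 3.3.2 lists "Time to permanent discontinuation of study medication due to any bleeding event" among four bleeding variables of specific focus; Protocol 2.4 and 12.2.2.1 list the same one.

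The censoring rule is in the last paragraph of SAP 4.1.1 and covers this variable together with the bleeding endpoints: "In safety time-to-event analysis of bleeding and discontinuation of study drug due to bleeding, patients not having suffered any bleeding event in the given category". Such patients are censored at whichever comes first of the study closure visit, last dose plus 7 days, death, last contact and consent withdrawal. The corresponding rule in Protocol 12.2.4 mentions bleeding only ("In safety time-to-event analysis of bleeding, patients not having suffered any bleeding event in the given category will be") and then gives the same list of cut-offs.

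For the estimator, SAP 4.2.6.2 states: "Time to bleeding event variables will be analysed using the same methodology as for the efficacy variables as described in Section 4.1". SAP 4.1 specifies a Cox model with treatment as the only factor, the count of patients with an event, and Kaplan-Meier estimates at a time point to be chosen from the available follow-up. It adds: "Kaplan-Meier estimates of the cumulative proportion of patients with events will be estimated and plotted". Protocol 12.2.1, which Protocol 12.2.2.1 applies to this endpoint, calls the same quantity a risk: "Kaplan-Meier estimates of the cumulative risk will also be presented".

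Neither document names a competing event or plans a cumulative incidence function. SAP 4.1.3 confines its informative-censoring checks to the primary efficacy endpoint.

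**The concern.** Kaplan-Meier treats a censored patient as someone who could still have the event later, and in effect shares that patient's future risk among those still followed. This is workable for the bleeding endpoints, because a patient off study drug can still bleed. It is not workable here. A patient who has finally stopped for dyspnoea, for another adverse event or by choice has no study drug left to stop. The same is true of a patient who dies on treatment.

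With those patients censored, 1 minus Kaplan-Meier describes what would happen if nobody ever stopped for another reason or died, and only if the different reasons for stopping were independent. It is not the cumulative proportion of patients with the event, which is how SAP 4.1 labels it. A reader who takes the curve as the share of patients coming off study drug because of bleeding will get too high a figure in both arms.

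**Working it through.** **Inputs from the documents.** Average follow-up 40 months, expected minimum 29, anticipated maximum treatment 58 (SAP 1.2); 19000 patients randomised 1:1 (SAP 1.3), so 9500 per arm. The plan gives no expected figure for this endpoint and no discontinuation rate for either arm, so there is nothing to reproduce. All rates below are assumptions.

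**Direction, without any rates.** Let b(u) be the hazard of stopping for bleeding and o(u) the hazard of a competing event, with cumulative hazards B and O.

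- 1 minus Kaplan-Meier targets the integral from 0 to t of b(u)·exp(−B(u)) du.
- The proportion who actually stop for bleeding is the integral from 0 to t of b(u)·exp(−B(u)−O(u)) du.

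The second integrand is never larger than the first, so Kaplan-Meier overstates as soon as anyone stops for another reason or dies on treatment. The 7-day extension barely matters. At 9 other stops per 100 patient-years it enlarges the risk set by about 0.09 × 7/365 = 0.17%. Simulation with the 7-day rule agreed with the formulas below to about 0.02 percentage points.

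**Size, with constant hazards.** With T in years:

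- 1−KM = 1 − exp(−bT)
- Cumulative incidence (CIF) = b/(b+o) × [1 − exp(−(b+o)T)]

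Example: ticagrelor, b = 0.015, o = 0.09, T = 40/12.

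- 1−KM = 1 − exp(−0.05) = 4.88%
- CIF = 0.015/0.105 × [1 − exp(−0.35)] = 0.1429 × 0.2953 = 4.22%
- Excess = 0.66 points

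At 40 months, with other stops as the only competing event (rates per 100 patient-years, ticagrelor / placebo):

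| Bleeding stops | Other stops | Ticagrelor 1−KM vs CIF | Excess, ticagrelor | Excess, placebo |
|---|---|---|---|---|
| 0.5 / 0.2 | 3 / 2 | 1.65% vs 1.57% | 0.08 | 0.02 |
| 1.0 / 0.3 | 5 / 4 | 3.28% vs 3.02% | 0.26 | 0.06 |
| 1.5 / 0.4 | 9 / 7 | 4.88% vs 4.22% | 0.66 | 0.14 |
| 2.0 / 0.6 | 12 / 9 | 6.45% vs 5.33% | 1.12 | 0.27 |

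If all 9500 patients were followed to 40 months, the standard error in the third row would be √(0.0422 × 0.9578/9500) = 0.21 points. Staggered follow-up makes the real one larger.

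**Time point.** For the third row on ticagrelor, the excess is 0.36 points at 29 months (3.56% vs 3.20%), 0.66 at 40 and 1.31 at 58 (6.99% vs 5.69%).

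**Death.** With an assumed 1.8 deaths per 100 patient-years as the only competing event, the excess on ticagrelor at 40 months is 0.05 to 0.19 points across the four bleeding rates.

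**Comparison of arms.** Take bleeding stops at 1.5 (ticagrelor) and 0.5 (placebo) and vary the other stops, again at 40 months:

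- Other stops 8 ticagrelor, 6 placebo: excess 0.59 vs 0.15 points; relative to the true proportion, 14% vs 10%.
- Other stops 6 ticagrelor, 8 placebo: 0.45 vs 0.20 points; relative, 10% vs 14%.
- Other stops 2 ticagrelor, 10 placebo: 0.16 vs 0.25 points.

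So the ordering of the arms depends on rates that the documents do not give.

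**The case against.** The strongest reply is that the plan already gives the reader what is needed. SAP 4.1 puts the number of patients with an event beside the Kaplan-Meier estimate. SAP 4.2.6 summarises reasons for and time to discontinuation by arm, and SAP 4.2.6.3 summarises adverse events leading to discontinuation. The Cox hazard ratio is valid as a cause-specific comparison. The variable is not the primary safety variable, and SAP 4.1 classes everything outside the confirmatory sequence as exploratory. All of this stands, and it limits the point to one estimate and one plot. It does not remove the point: with follow-up expected to run from 29 to 58 months, a crude percentage is not a risk at a stated time, and the only planned fixed-time figure and the only plot are the overstated ones.

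It is also fair that not every stop competes. Protocol 5.8.3.4 encourages restart even after a premature discontinuation visit, and the censoring clock runs from the last dose. A patient who stops for dyspnoea, restarts and later stops for bleeding can have the event; only the final stop precludes it.

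A reader might infer three further things that the documents do not support:

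- *That the overstatement is certainly larger on ticagrelor.* Protocol 1.4 reports more TIMI Major bleeding than placebo in an earlier trial and names dyspnoea as a common adverse event. Protocol 3.2 reports fewer discontinuations on 60 mg, but compared with 90 mg. None of this is a discontinuation rate by arm.
- *That a planned risk difference or number needed to harm is wrong.* Neither document plans one for this endpoint.
- *That the SAP hid a change from the protocol.* The SAP amendment history for March 2017 records that the bleeding rule was extended to this endpoint, and Protocol 12.2.2.1 already lists the endpoint under bleeding events.

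**Conclusion.** The point holds for the Kaplan-Meier proportion and its plot, for this one endpoint. That 1 minus Kaplan-Meier overstates the proportion stopping for bleeding follows from the definitions and needs no assumed rate.

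Its size does depend on assumed rates. With constant hazards and the ranges tried, the excess on ticagrelor at 40 months is roughly 0.1 to 1.1 percentage points, and it is larger if a later time point is chosen. The excess in percentage points is probably larger on ticagrelor, because more bleeding is expected there, but the documents cannot show this. In relative terms it would be larger on ticagrelor only if competing stops are more frequent there.

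The hazard ratio, the crude counts and the confirmatory tests are untouched. This is a modest but systematic error in a focus safety display, and it is cheap to remove.

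**What to change.** In SAP 4.1.1 and 4.2.6.2, for time to permanent discontinuation due to bleeding only:

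- Replace 1 minus Kaplan-Meier with the Aalen-Johansen cumulative incidence, reported and plotted by arm. Treat final permanent discontinuation for any other reason, and death on treatment, as competing events. The planned end of treatment at study closure stays a censoring event.
- Keep the planned Cox model and label its result a cause-specific hazard ratio.
- Word the censoring condition as *not permanently discontinued due to bleeding*. The present condition concerns having had a bleeding event, and does not describe a patient who bled but stayed on study drug.

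The cost is a few lines of SAP text and one extra standard procedure. The reason for stopping and the date of last intake are already recorded (Protocol 5.8.3 and 5.9), so no new data are needed. The reported proportion will be slightly lower than under the current plan.
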